6.0 Procedures Involved*

6.1 *Describe study procedures.*

Study Overview: We propose two phases of study activities. **Phase 1** (Aim 1) comprises 12 months of collaboration with survivor/family working groups to develop: targeted letters, choice options for relative outreach, and content for an interactive website, and short cueing messages that engage ovarian cancer survivors and their at-risk relatives in considering genetic risk assessment. **All of these study materials will be submitted as an IRB amendment prior to fielding.** **Phase 2** (Aims 2-3 – Years 2-4), is an RCT that compares the message-based intervention (MBI) with current standard outreach. We will evaluate the following outcomes: survivor reach, at-risk relative reach, and uptake of appropriate cancer genetic services and conduct a process evaluation based on the RE-AIM framework that includes survivors and relatives (Aim 3).

A. Aim 1: Develop a scalable message-based outreach intervention.

A.1. Overarching Approach: We base our community partnerships on the combined principles and methods of community-based participatory research and citizen science.²¹ We propose to bring the issue of increasing reach to the community of ovarian cancer survivors and families and engage their collaboration to develop appealing messages to expand the reach of genetic services to survivors and close relatives. Community members with relevant experience will work with us as citizen scientists using their experiences and skills to help develop messages.²¹ We will hone ovarian cancer survivor/family partners' skills as citizen scientists by familiarizing them with theories of information processing, relational autonomy and distributive justice (see below). The overarching objective is to co-create content that has the greatest potential to engage survivors/relatives to thoughtfully consider the tradeoffs of genetic service uptake. [name], [name] and Peachtree Solutions have considerable experience working with community advisory boards (CABs) and end users. [name] has conducted qualitative research to develop genetic risk messages in a variety of settings in the U.S. and abroad.²²⁻²⁴

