A.3. Working Group Procedures: [name] who has experience working with community groups and evaluating websites that link those with inherited disease to genetic services will oversee working group activities.²⁵ In *iteration 1*, one community working group will recommend approaches for framing the “large ask” and choice sets for relative contact options. A second and third working group will assist in collecting survivor-family stories using photonovela or other strategies. In *iteration 2*, content experts in communication, genetics and ethics will assemble working group content and develop initial formats for the website and print materials. Communication and bioethics experts will review materials for alignment with communication frameworks and ethical principles. Next, Peachtree Solutions (see letter of support), our web-development partner, will work with Emory’s Visual Medical Education team to draft the website and print materials. In *iteration 3*, a third community working group will review initial and revised iterations of intervention content using systematic cognitive interviewing methods.²⁶ Peachtree Solutions has extensive experience with the latest usability standards and will direct the usability testing. The investigative team and consultants will make revisions based on each round of panel input. We will use the Suitability Assessment of Materials (SAM) and Comprehensibility (CAM) scale to evaluate the readability and comprehensibility of the website with the aim to develop a website that users’ rate as “superior”, indicating it is easy to use and understand, low in cognitive demand, attention-getting, and motivating.²⁷

Prior to fielding the trial, we will submit the developed study materials as part of IRB amendment.

[figure not shown]
B. Aim 2: Conduct a two-arm randomized intervention trial (N~2,918).

B.1. Study Design: We will compare the message-based intervention (MBI) developed in Aim 1 to standard outreach in a two-arm RCT in Years 2 and 3. The MBI comprises a combination of novel intervention components that depart sufficiently from prior research to warrant a comparison arm (with access to the MBI website when the trial period is completed).²⁸ Figure 2 displays the flow of the intervention.

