B.6.1. Survivor components: GCR will mail survivors a standard letter and log-in information. Survivors will have access to a condensed version of the website that includes information on: genetic risk and genetic counseling, patient navigators in their locale, and the importance of conveying information to close relatives. Survivors will be provided with 2 extra letters and login information for 2 close relatives. Survivors can request additional relative letters/logins for any relatives that they would like to involve on the website or the GCR.

B.6.2. Close relative components: The standard family letter shared by the survivor will provide login codes for the relative to visit the condensed website with information about genetic risk and the value of completing the online B-RST™ screener.

All survivors and relatives in the standard arm will have access to the telegenetic counseling services described above. After completion of intervention trial, all survivors in the standard outreach arm regardless of their study participation will have access to the MBI sections of the website.

6.2 *Procedures being performed to monitor participants for safety or minimize risks.*

We expect the research-related risk to be minimal: the probability & magnitude of harm/discomfort anticipated in the research is no greater than those ordinarily encountered in daily life or during the performance of routine physical or psychological examinations/tests.

There are no anticipated physical risks of participating in this study. However, participants may experience psychological or emotional distress from participating in the study, particularly activities related to the way their family interacts or communicates about ovarian cancer and genetic risks. Survivors may worry about their family members' emotional distress. Participants whose motivations for study

enrollment include histories of ovarian cancer in either themselves or their family members may find it upsetting to re-visit their personal experiences.

There is a small potential risk of outreach to family members of a recently deceased woman. In GCR's past experiences, this event does indeed happen on occasion but the typical response is a family member contacts GCR to inform about the passing of their family member. No adverse event has been reported thus far (e.g., distress, confusion). The proposed research activities present the same outreach risk (which is minimal) as routine contact by the GCR.

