Primary RCT outcomes: 1) Survivor reach: the proportion of the eligible survivors identified and contacted by GCR who log in to the website, 2) Close relative reach: the proportion of close relatives enumerated by survivors who log in to the website, and 3) Uptake of cancer genetic services: the proportion of untested survivors who complete telegenetic counseling and the proportion of relatives enumerated who complete B-RST™ screening and subsequently access genetic counseling. We will evaluate secondary outcomes: In the MBI arm, we will track survivor’ and relatives’ patterns of website usage including: duration of time on the website, number of return visits, pages viewed, and the proportion of survivors who select different relative contact options. We can also link survivor and relative patterns of use to evaluate “family” patterns of use. We will assess the proportion of survivors and relatives who self-report in the post-intervention online survey (described below) having completed genetic testing, but we will not have sufficient power to consider uptake of genetic testing as a primary outcome.

Primary data sources include: 1) GCR will record all survivor contacts (i.e., mailings, calls, messages left, call-backs), 2) website use reported by Peachtree Solutions on a monthly basis (i.e., website login and user-patterns data), and 3) genetic counseling interns’ electronic case

logbook of appointment scheduling and completion. We will limit website data collection to information regarding survivor's prior genetic counseling/testing, enumeration of relatives, and contact information for relatives with survivors' approval to contact. We will limit data collected from relatives on the website to telephone number, home address, email addresses, and to prior experiences with genetic counseling/testing. We decided against a formal survey prior to or during the intervention to minimize participant burden and to enable a cleaner evaluation of the feasibility of using the proposed intervention to maximize survivor/relative reach.

Post-intervention online survey: We will recruit survivors and relatives who logged on to the website, regardless of their level of participation. We will post a study invitation letter and a one-time 20-minute survey on the study website and send the letter to survivors and relatives with contact information (e.g., mailing address, email, or mobile phone number) about 4 weeks after the intervention phase.

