Aim 2 (message-based intervention (MBI) and waitlist standard outreach approaches): Ovarian cancer survivors in the Georgia Cancer Registry (GCR) database who meet the following criteria will be considered for study participation: 1) diagnosed with ovarian, fallopian tube, or peritoneal cancers; 2) lived in Georgia at the time of diagnosis; 3) currently are alive per the registry's records; and 4) have a mailing address. The proposed recruitment procedures comply with GCR's current standards and are adapted from strategies that were effective in other studies using cancer registry for recruitment.¹⁻⁵ We will classify survivors who log in to the study website as recruited. Recruitment will rely on multiple communications aimed to encourage survivors to log in to the study website; the number of contacts will be largely identical for both arms: first mail-out (full packet plus \$10 incentive), telephone contact from a trained GCR staff, second mail-out (postcard reminder), and third mail-out (full packet). Our review of registry files as of May 2019 showed that: of the 8,760 women with a diagnosis of ovarian, fallopian tube, or peritoneal cancer (excluding those who were deceased or lost to follow as of 2017), we will have addresses for about 2,918 survivors over the 16-month recruitment period. In a recent study using GCR to recruit breast cancer survivors in Georgia with registry standard mailing and phone contact without financial compensation, 63% agreed to participate.⁶ A conservative assumption of reaching (i.e., log in to the study website) 45% in the MBI arm versus 10% in the standard outreach arm, we need to recruit 801 cancer survivors into our study. Relatives of survivors eligible to participate must be: 25 years or older, have access to the internet, be a first- or second-degree relative of the survivor, able to read English, and not be incarcerated or institutionalized. We estimate that 801 cancer survivors will log in to the website and 75% of them (N=601) will enumerate a median of 2 at-risk relatives. We assume the number of at-risk relatives enumerated will not differ between intervention arms. Furthermore, we estimate that 40% of relatives referred by MBI arm participants will log on compared to 20% in the standard outreach arm. We expect that about 438 relatives will participate in the study. Recruitment of survivors and relatives for the intervention will occur in Year 2 and 3.

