Aim 2 & 3 (post-intervention online survey): We will recruit survivors and relatives who logged on to the website, regardless of their level of participation. We will post a study invitation letter and a one-time 20-minute survey on the study website and send the letter to survivors and relatives with contact information (e.g., mailing address, email, or mobile phone number) about 4 weeks after the intervention phase. Based on our sample size scenarios we estimate recruiting 120 survivors (15% response rate) and 66 relatives (15% response rate) to complete the online survey. We will compensate participants with \$35 to complete the online survey. In other research, we have used an online survey to evaluate recall of B-RST™ results following a mammogram screening visit; 35% agreed to complete an online survey with a \$25 incentive.⁷ Recruitment of survivors and relatives for the online survey will take approximately 3 months at the beginning of Year 4.

Aim 3 (mail survey to survivors who did not login to the study website): GCR will send a brief survey to survivors in both study arms who have never accessed the website after GCR completes recruitment efforts. Based on our prior recruitment data, about 1,686 survivors will not visit the study website by Jan, 2023 and will be eligible for this survey. We will conduct staged selection

[figure not shown]

of 650 non-responders over the 8-month recruitment period (Jan – Aug 2023): (1) reach out to all participants with a confirmed phone number (GCR have talked to participants during trial recruitment or their voicemail states their name); 2) reach out to all participants with a confirmed mailing address (GCR confirmed the mailing address through at least two resources (GCR database, ACCUR or voter registration database); and 3) reach out to participants whose ovarian cancer diagnosis is within five years. We aim to recruit 375 survivors for this survey. The proposed recruitment procedures comply with GCR's current standards. Recruitment will rely on two rounds of communications aimed to encourage non-responders in both study arms to complete the survey (Figure 4).

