analyses of survey data to characterize participants' processing and demographics. We will apply linear or logistic regression to compare differences on knowledge, comprehension, between the intervention and standard outreach arms. For example, in these analyses we will evaluate whether participants in the MBI arm show higher cancer genetic knowledge than relatives in the standard outreach arm. Overall, we will adjust these analyses for health literacy and age.

User Pattern Analysis: To assess patterns of website use and identify sub-groups of users, we will use traditional web tool user data (e.g. time of access after invite to use, frequency of use) and programmatic user data (e.g. types of viewed content, types of completed tasks). These analyses will be conducted approximately 2/3 of the way through recruitment when we have adequate numbers for characterizing user patterns. We will identify the sub-groups through descriptive analysis and if meaningful using cluster analysis.⁷⁰ Subsequently, we will use multinomial regression analysis to understand sociodemographic differences in cluster members and use the clusters as strata for the recruitment into the online discussion forum described above.

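### Standard-arm survivors may be given the MBI website before or during the post-intervention survey that compares the arms, because the access date is not tied to survey closure

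*Combined protocol and SAP*

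**What the plan says.** **Access rule.** The protocol gives it twice in section 6.1. B.1 describes a comparison arm "with access to the MBI website when the trial period is completed". B.6.2 says: "After completion of intervention trial, all survivors in the standard outreach arm regardless of their study participation will have access to the MBI sections". Neither place gives a date or mentions the survey.

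**Trial dates.** B.1 compares the MBI "to standard outreach in a two-arm RCT in Years 2 and 3", and the access rule follows in the next sentence. Section 13.0 agrees: "Recruitment of survivors and relatives for the intervention will occur in Year 2 and 3". The study overview in section 6.1 is broader and describes Phase 2 as ("Aims 2-3 – Years 2-4), is an RCT that compares the message-based intervention (MBI) with current standard outreach".

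**Survey.** Section 6.4 says: "We will post a study invitation letter and a one-time 20-minute survey on the study website". The letter is also sent to those with contact details about four weeks after the intervention phase. Section 13.0 adds: "Recruitment of survivors and relatives for the online survey will take approximately 3 months at the beginning of Year 4". Section 9.1 invites people in both arms who logged in.

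**Analysis.** Section 17.0 uses linear or logistic regression to "compare differences on knowledge, comprehension, between the intervention and standard outreach arms", adjusting for health literacy and age.

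**The concern.** A waitlist design protects a comparison only while the control arm is still waiting. If the trial ends with Year 3 and access opens then, the survey falls after the crossover. A standard-arm survivor would return to the study website to answer it when the MBI sections are already open to her.

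Control respondents who read that material first would move toward the MBI arm on knowledge, comprehension and related survivor measures. The contrast would shrink toward zero. A small or null difference could then reflect a weak intervention, early crossover, or both, and the planned analysis has no term that would separate them.

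The survey supplies the information-processing evidence on how the MBI might work. It is not the source of the primary outcomes, and that limits what is at stake.

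**Working it through.** **1. Order of events**

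| Event | Timing in the protocol | Where |
|---|---|---|
| Two-arm trial | Years 2 and 3 | 6.1, B.1 |
| Intervention recruitment | Years 2 and 3 | 13.0 |
| Standard-arm survivors get MBI sections | When the trial is completed; no date | 6.1, B.1 and B.6.2 |
| Survey invitation | About 4 weeks after the intervention phase | 6.4 |
| Survey recruitment | About 3 months, start of Year 4 | 13.0 |

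If completion means the end of the Years 2 to 3 trial in B.1, access comes before the invitation and stays open throughout the survey. No section holds access back until the survey closes. The survey model has no exposure variable.

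**2. Survey size.** The plan's totals reproduce.

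- Logins: 1,459 x 0.45 = 656.6 and 1,459 x 0.10 = 145.9. Rounded down these are 656 and 145, which sum to 801 (section 17.0).
- Survivor respondents: 801 x 0.15 = 120.2, against 120 stated in section 6.4.
- Relative respondents: 438 x 0.15 = 65.7, against 66 stated.

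The plan gives no split by arm. Assuming the same 15% response in each:

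- MBI survivors: 656 x 0.15 = 98.4, about 98.
- Standard-arm survivors: 145 x 0.15 = 21.75, about 22.

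**3. Illustration of dilution.** Let d be the true difference in SD units. Let c be the share of the MBI effect that control respondents gain through early access. The documents give neither.

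- Observed difference = d x (1 - c).
- Standard error = sqrt(1/98 + 1/22) = 0.236 SD.
- Power, two-sided 0.05 (assumed) = Phi(d(1 - c)/0.236 - 1.96).
- Difference detectable with 80% power = (1.96 + 0.84) x 0.236/(1 - c).

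| c | Power, d = 0.50 | Power, d = 0.65 | Detectable true difference (SD) |
|---|---|---|---|
| 0 | 0.56 | 0.79 | 0.66 |
| 0.10 | 0.48 | 0.70 | 0.73 |
| 0.25 | 0.36 | 0.54 | 0.88 |
| 0.50 | 0.18 | 0.28 | 1.32 |

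If viewing gave the full effect at once, c = 0.25 would correspond to 22 x 0.25 = 5.5, that is five or six women.

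**4. Primary outcomes.** Table 3 power reproduces at above .99 for all four rows, with the plan's design effect of 1.3 for relatives. Those outcomes rest on website and counseling logs, not the survey. They are safe from this problem if counting stops before access opens, but no cut-off date is stated.

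**The case against.** The strongest reply is that the order is not stated. Completion has no date. The overview in section 6.1 calls the whole of Phase 2, Years 2 to 4, a randomised trial, and section 6.3 lists the survey among the Aim 2 data sources. On that reading the trial ends only after the survey and there is no overlap. This stands as a possible reading. It is the less natural one: the overview also covers the process evaluation, whereas B.1 dates the comparison itself and sets the access rule in the next sentence.

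Three further points stand.

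- **Access is not use.** Nothing says when standard-arm survivors are told of the MBI sections, or that the survey route passes through them. Section 22.0 sends respondents from the consent form to the survey link.
- **The rule names survivors only.** Several survey measures suit relatives better. The information acceptance scale is described for relatives, and recall of the B-RST result belongs to the relatives' screener. Section 17.0's own example of the contrast refers to relatives in the standard arm.
- **The survivor contrast is weak anyway.** With 98 and 22 respondents it reaches 80% power only at about 0.66 SD with no contamination at all.

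A reader might infer that the comparator is certainly contaminated, that a null survey result would be uninterpretable for this reason alone, or that the survey is the only arm-level evidence on these constructs. The documents do not support any of these. Use of the MBI pages is unknown and small numbers already limit a null result. Section 6.4 also has testing completion tracked electronically, and section 17.0 treats sessions and time on the website as indicators of central processing and compares recorded counseling sessions by arm.

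**Conclusion.** The concern holds as a risk, not as an established fault. On the most natural reading of the dates, standard-arm survivors may gain the MBI sections before or during the survey, and nothing in the plan prevents or accounts for it. Any resulting bias in the survivor comparison would run toward no difference, assuming the MBI improves the measures concerned.

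The size cannot be known from the documents. The power figures illustrate only how sensitive a control group of about 22 would be. They rest on equal 15% response by arm, a two-sided 0.05 level, effects of 0.50 to 0.65 SD and c from 0 to 0.50, all assumed apart from the overall 15%.

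Severity is minor to moderate, because a secondary and already imprecise comparison is affected. Confidence is moderate, because the order is inferred.

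**What to change.** 1. In B.1 and B.6.2, state that standard-arm access to the MBI sections opens only after the post-intervention survey has closed in both arms and after the data cut-off for the primary outcomes. Give that cut-off a date or a defined trigger.
2. Have the web developer log the date each standard-arm login is opened, and any MBI page use before survey completion.
3. In section 17.0, keep every respondent in the arm comparison as randomised. Use the log only for a pre-specified sensitivity analysis. Leaving out standard-arm surveys completed after access opened would be a post-randomisation exclusion in one arm only: it could bias the contrast and would shrink a group of about 22.

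**Cost.** A few sentences of protocol text, one access setting and a log. Standard-arm survivors would receive the MBI pages about three to four months later (the survey's three months, plus up to four weeks before it). Telegenetic counseling, which B.6.2 already offers to the standard arm, stays available to them throughout.

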
B.5.2. Close relative procedures: Relatives eligible to participate must be: 25 years or older (age recommended to initiate preventive behaviors)⁶⁰, able to access the internet, a 1st or 2nd degree relative of the survivor, able to read English, and non-incarcerated or institutionalized. Relatives will receive a unique website login linked to the survivor that enables access to the website content and describes pros/cons of family-history-based genetic risk screening for HBOC. Additionally, relatives for whom we have cell phone numbers will receive 3 cueing SMS reminders over 9 weeks (developed during Aim 1). The SMS will thank them for visiting the website and

suggest they return as needed and complete the genetic risk assessment for ovarian cancer family history. We will use the B-RST™ (developed and validated by [name] in 2009),^{61,62} which is endorsed by the USPSTF as one of several validated screening tools that is clinically useful for estimating the probability of *BRCA1/2* mutation and identifying women for referral to genetic counseling. This screener assesses personal and family history (1st and 2nd relatives) of breast cancer, bilateral breast cancer, ovarian cancer and male breast cancer, and Ashkenazi Jewish heritage. The intervention website will include a separate portal dedicated to the B-RST™ 3.1 screen. Although all 1st or 2nd degree relatives of ovarian cancer survivors will screen positive on B-RST™, completing the screener will raise participant awareness of the factors that contribute to hereditary risk of ovarian cancer and will reinforce the salience of seeking genetic counseling. We will recommend genetic counseling for all close relatives because of their heightened risk for carrying a *BRCA1/2* mutation. We will direct interested relatives to the same telegenetic counseling services provided to survivors. Ideally, we would recommend testing the survivors first, and only offer genetic testing to close relatives with a confirmed pathogenic variant ala cascade testing. However, we will offer genetic testing to relatives regardless of survivor's testing status.

B.6. Standard Outreach Arm

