Based on our sample size scenarios in [Table 3](#) we estimate recruiting 120 survivors (15% response rate) and 66 relatives (15% response rate) to complete the online survey. We will compensate participants with \$35 to complete the online survey. In other research, we used an online survey to evaluate recall of B-RST™ results following a mammogram screening visit; 35% agreed to complete an online survey with a \$25 incentive.⁶³ We will include measures of ([Table 2](#)): Ability to process health information ("How confident are you filling out medical forms by yourself?") This item correlates strongly with longer health literacy assessments¹⁴²; We will assess central processing in several domains: a 7-item breast/ovarian cancer genetic knowledge scale¹⁴³, recall of the B-RST™ result (correct/incorrect), accuracy of perceived likelihood of carrying a *BRCA1/2* mutation, and accuracy of perceived absolute risk of ovarian cancer ("how likely is that you will develop ovarian cancer in your lifetime?").⁶³⁻⁶⁵ We will assess defensive processing with a 9-item information acceptance scale in which relatives respond to statements such as, "The information I received about my risk for hereditary breast and ovarian cancer seems accurate" (scores range from 0-45, a higher score indicates a high acceptance)⁶³. Cancer fear is based on 3-items (e.g., "of all the diseases, I am most afraid of cancer.")⁶⁶ We will assess comparative risk perception with a single item "compared to the average woman your age, would you say that you are less likely/as likely/more likely to develop ovarian cancer." Prevention efficacy: We will assess ovarian cancer fatalism with two items (e.g., "If a woman is meant to get ovarian cancer, she will get it no matter what she does?").⁶⁶ Other measures: cancer genetic testing (yes/no), extent of family discussions about ovarian cancer, and relevant demographics.³⁰

Table 2. Post-Intervention Online Survey Data Collection

Component	Measures
Ability to process health information	health literacy
Central processing	Breast/ovarian cancer knowledge, accuracy of perceived risk for BRCA1/2 mutations and ovarian cancer
Defensive processing	Accept information as accurate, cancer fear, cancer risk perception
Prevention efficacy	Endorsing statements that ovarian cancer risk can be reduced
Reactions to the intervention	Acceptability and votes on outreach communication approaches

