12.0 Local Number of Participants

1240

Planned (Anticipated)

Racial Categories	Ethnic Categories				Total	
	Not Hispanic or Latino		Hispanic or Latino			
	Female	Male	Female	Male		
American Indian/Alaska Native	4	1	0	0	5	
Asian	35	6	4	1	46	
Native Hawaiian or Other Pacific Islander	1	0	0	0	1	
Black or African American	302	53	33	7	395	
White	591	102	66	11	770	
More than One Race	18	3	2	0	23	
Total	951	165	105	19	1240	

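### The survey's two ovarian-cancer risk items do not fit survivors or male relatives, B-RST recall fits only relatives who completed the screen, and the planned arm comparison ignores role

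*Combined protocol and SAP*

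**What the plan says.** Section 6.4 sends one survey to both groups: "We will recruit survivors and relatives who logged on to the website, regardless of their level of participation". Among its measures are:

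- absolute risk, scored for accuracy: "accuracy of perceived absolute risk of ovarian cancer ('how likely is that you will develop ovarian cancer in your lifetime";
- comparative risk: "compared to the average woman your age, would you say that you are less likely/as likely/more likely to develop ovarian cancer";
- B-RST recall: "recall of the B-RST™ result (correct/incorrect".

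No respondent group or skip rule is given for any of the three. The only scale worded for one group is the "9-item information acceptance scale in which relatives respond to statements such as". Table 2 lists accuracy of perceived ovarian-cancer risk under central processing and cancer risk perception under defensive processing. B-RST recall appears in the 6.4 text but not in Table 2.

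The expected yield is stated as follows: "we estimate recruiting 120 survivors (15% response rate) and 66 relatives (15% response rate) to complete the online survey".

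On who these people are, section 6.1 (B.2) requires survivors to have an ovarian, fallopian tube or peritoneal cancer diagnosis. The eligibility criteria for relatives (6.1 B.5.2 and section 13.0) contain no sex criterion, and the enrolment table in section 12.0 reads "Total 951 165 105 19 1240", the second and fourth figures being men. The consent section (22.0) directs every consenting relative to the B-RST, and B.5.2 states that "all 1st or 2nd degree relatives of ovarian cancer survivors will screen positive on B-RST™".

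Section 17.0 compares arms on the survey measures by linear or logistic regression, adjusted for health literacy and age. It gives no restriction or adjustment by role or sex. Its worked example sets MBI participants against standard-arm relatives, which leaves the analysis set unclear.

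**The concern.** A score for accuracy needs a true value to compare with. For a survivor asked whether she will develop ovarian cancer, the plan gives none. For a man the question does not apply, and the comparative item is worded for women. If all respondents are scored, most of these scores carry no information about comprehension.

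The second problem is the arm comparison. The MBI is expected to bring in proportionally more relatives than standard outreach. Any measure on which survivors and relatives differ will then differ between arms even if the intervention changes nobody's understanding. Health literacy and age do not stand in for role.

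B-RST recall has a narrower version of the same difficulty. Survivors have no planned B-RST result, relatives who log in without completing the screen have none either, and everyone who does have a result has the same one.

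At stake is the explanation of how the intervention works through central and defensive processing, not the test of whether it works.

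**Working it through.** **The plan's own survey figures.** Section 17.0 expects 801 survivors to log in (656 MBI, 145 standard). Table 3 gives 394 + 44 = 438 relatives. At 15% response, 0.15 × 801 = 120.2 and 0.15 × 438 = 65.7. The stated 120 and 66 reproduce, for a total of 186.

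**Risk items: share of respondents outside the group they fit.**
- Survivors: 120 / 186 = 64.5%.
- Let m be the male share of responding relatives. The share outside is (120 + 66m) / 186.
- m = 0: 64.5%. m = 0.25: 136.5 / 186 = 73.4%. m = 0.50: 153 / 186 = 82.3%.
- Planned men (section 12.0): 165 + 19 = 184. If all are relatives (801 + 438 = 1,239, against a planned 1,240), m = 184 / 438 = 42.0%. Men are then 66 × 0.420 = 27.7 respondents, and female relatives 66 − 27.7 = 38.3 (20.6% of 186). The share outside is (120 + 27.7) / 186 = 79.4%.
- By arm, on the same assumptions: 0.15 × 394 × 0.580 = 34.3 MBI and 0.15 × 44 × 0.580 = 3.8 standard. These counts still include any female relative who has herself had ovarian cancer.

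**Role mix by arm, with equal response in all groups.**
- MBI: 656 / (656 + 394) = 656 / 1,050 = 62.5%, about 62% before rounding (0.6248).
- Standard: 145 / (145 + 44) = 145 / 189 = 76.7%, about 77%.
- Suppose the proportion scored accurate is s in survivors and r in relatives, the same in both arms. The unadjusted arm difference, MBI minus standard, is then (0.767 − 0.625) × (r − s) = 0.142 × (r − s). Every 10 points between roles produces about 1.4 points between arms with no effect on comprehension.

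**B-RST recall: who has a result.**
- Table 3 uptake: 0.70 × 394 = 275.8 and 0.30 × 44 = 13.2, total 289; 289 / 438 = 66.0% of relatives who log in.
- Survey respondents with a result: 66 × 0.660 = 43.5, about 44. By arm: 0.15 × 275.8 = 41.4 and 0.15 × 13.2 = 2.0.
- Without a result: (186 − 43.5) / 186 = 76.6%, made up of 120 survivors and about 22 relatives.
- By B.5.2 the true result is positive for all of the roughly 44.

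**The case against.** The strongest reply is that no finished instrument exists. Sections 6.4 and 13.0 say the survey instruments will be developed in the planning year and submitted later. Section 6.4 is a list of measures, not a routed questionnaire; one scale is already worded for relatives, and Table 2 collects personal cancer history, which would help restrict the items. No sentence says every item is scored for every respondent. This stands in part: a reader might infer a proven instrument defect, and the documents do not show one. But 6.4 already fixes wording and accuracy scoring for these items, and section 17.0 already fixes the covariates. Followed as written, they give the results above.

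Three other stronger readings are tempting and should be set aside.

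- *That men have no B-RST result to recall.* Section 22.0 directs all consenting relatives to the screen, B.5.2 expects all to screen positive, and male breast cancer is among its history items. A man who completes it has a result.
- *That a constant positive result makes recall uninterpretable.* Among completers, someone reporting a negative result has misremembered or rejected it, which matters in a study concerned with denial and avoidance. The limit is that correct recall cannot be told apart from a default positive answer, and false-positive recall cannot be detected.
- *That the processing constructs collapse.* The 7-item knowledge scale, perceived *BRCA1/2* likelihood, the acceptance scale and the cancer-fear items remain, and section 17.0 uses genetic knowledge as its worked example.

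It is also fair to say that none of these items is a primary or listed secondary outcome (section 4.1).

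**Conclusion.** The point holds for the two ovarian-cancer risk items and for the arm comparison that ignores role, and in limited form for B-RST recall. At least 65% of expected respondents fall outside the group the risk items fit. That floor needs only the plan's own 120 and 66. The upper figure of 82% assumes half of responding relatives are men. The 79%, and the split of about 34 against 4, further assume that all 184 planned men are relatives and that response is equal by sex and arm; section 12.0 does not split men by role, so these should be read as one scenario within the range. The 62% and 77% role shares assume the Table 3 rates and equal response in all groups. The 44 completers (about 41 and 2 by arm) also assume response does not depend on having completed the screen.

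A reader might infer that the trial's main conclusions are threatened. They are not: reach and uptake are measured from website and counseling records, so the problem is confined to survey and process measures.

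**What to change.** Amend section 6.4, Table 2 and the survey analysis paragraph in section 17.0:

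1. Show and score the two ovarian-cancer risk items only in female relatives without ovarian cancer, and report them descriptively by arm.
2. Limit B-RST recall to relatives who completed the screen, report it descriptively, and state that all true results are positive. This belongs in the 6.4 text, since Table 2 does not list the item.
3. For survey measures valid for all respondents (the knowledge scale and perceived *BRCA1/2* likelihood), adjust or stratify the arm comparison by role, survivor or relative.
4. Record sex explicitly. Table 2 does not name it, although its list of demographics is open-ended.

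The cost is skip logic in an instrument still to be developed and a few lines of analysis text. The downside is a small N for the restricted items, about 38 and 44 with very few in the standard arm, which is why description rather than testing is proposed. The survey is given once with no baseline, so the rules should be set before it is fielded. Dropping B-RST recall or writing a substitute risk item is optional.
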